12.1.6 Physical Examination

Physical examinations will be conducted according to the schedule described in [Appendix A](#) and [Appendix C](#). Breast, rectal, and urogenital exams are not required unless warranted based on the clinical judgment of the patient's medical history or current medical condition. The physical exam should be done by a physician or physician's assistant or similarly qualified individual. At some visits a Directed Physical Examination will be performed. These exams will be focused on assessment of any patient complaints and concerns.

12.1.7 Chest X-ray

Chest X-rays (CXR) will be performed according to the schedule described in [Appendix A](#) and [Appendix C](#). [Post-baseline CXRs will be taken](#) to assess for presence of or changes in interstitial lung disease (ILD) compared to baseline CXR.

12.1.8 **Laboratory Assessments**

All laboratory assessment will be conducted according to the schedule described in [Appendix A](#) and [Appendix C](#). Procedures for processing samples are included in the Study Operations Manual.

12.1.8.1 **Hematology**

Hematology assessments will include white blood cells (WBC) count with differential, red blood cell (RBC) count, hematocrit (Hct), hemoglobin (Hgb), and platelet (Plt) count.

12.1.8.2 **Blood Chemistry**

Clinical chemistry assessments will include alkaline phosphatase, alanine aminotransferase (ALT), aspartate aminotransferase (AST), total bilirubin, blood urea nitrogen (BUN), creatinine, fibrinogen, glucose (fasting), and electrolytes (sodium, potassium, chloride, bicarbonate, phosphate, and magnesium), and urine for urine-albumin-creatinine ratio (UACR). If the UACR cannot be calculated due to the microalbumin analysis being below the limit of quantification for the analytical method (eg. <12 mg/dL), the low microalbumin can be used as a surrogate for an acceptable UACR.

12.1.8.3 **Glomerular Filtration Rate (GFR)**

Estimated glomerular filtration rate (eGFR) will be calculated according to the Study Operations Manual.

12.1.8.4 **Lipids**

Fasting lipid assessments will include total cholesterol, high-density lipoprotein (HDL), low-density lipoprotein (LDL), and triglycerides.

12.1.8.5 **Coagulation**

Coagulation assessments will include prothrombin time (PT), activated partial thromboplastin time (aPTT), international normalized ratio (INR).

12.1.8.6 **Antibody Assessments**

Blood samples will be collected for assessment of antibody development to pegadricase and uricase, and for neutralizing antibodies and anti-pegadricase point of service validation. All blood samples for assessment of antibody development are required to be collected prior to study drug dosing. Antibody samples collected after the screening period will be assessed only in patients in active treatment arms.

12.1.8.7 **COVID-19 Testing**

Patients with COVID-19 infection can experience a range of clinical manifestations, from no symptoms to critical illness.

Screening Visit:

During Screening, all patients should be tested for COVID-19 by an FDA Emergency Use Authorized COVID-19 molecular assay for detection of SARS-CoV-2 RNA. A patient with a positive test result is permitted to request re-testing. A patient who requests re-testing should wait at least 10 days after the date of the first positive COVID-19 diagnostic test, as long as no symptoms have developed. If the

second test is positive for COVID-19, then the patient will be excluded from enrollment. If the second test is negative for COVID-19, then the patient must be tested a third time at least 24 hours after the second test to confirm the negative result.

On Study:

Once a patient is enrolled in the study, the investigational site will manage the patient according to its institutional standards and procedures established for COVID-19. During the study, a patient presenting with both symptoms (only severe and critical illness as per definitions below) of COVID-19 and positive COVID-19 test results will be discontinued from study treatment. The patient will be permitted to resume study visits for continued assessments (but not treatment with SEL-212 or placebo) according to the institutional standards and/or procedures of the investigational site.

Patients with mild-moderate COVID-19 illness (as per definitions below) will be allowed to resume study visits (on treatment with SEL-212 or placebo) after resolution of acute symptoms of clinical disease (except for loss of smell and taste) and meeting quarantine requirements so long as their subsequent dose occurs ≤90 days from their prior dosing day as per section 7.4.1.1. Patients with mild-moderate COVID-19 illness can continue **non-dosing study visits** as per protocol mandated visit window prior to resolution of acute symptoms according to the institutional standards and/or procedures of the investigational site.

Enrolled patients in the study with mild-moderate COVID-19 illness can be treated with anti-SARS-CoV-2 monoclonal antibodies. These patients will be allowed to resume study visits (on treatment with SEL-212 or placebo) after 2 weeks of receiving monoclonal antibodies, and confirmation of resolution of acute symptoms of clinical disease (except for loss of smell and taste), and meeting quarantine requirements so long as their subsequent dose occurs ≤90 days from their prior dosing day as per section 7.4.1.1.

Regardless of COVID-19 disease severity, enrolled patients in the study who are treated for COVID-19 with anti-viral therapy (including Remdesivir), anti-cytokine therapies (including anti-IL-6 or anti-IL-1 therapy), or JAK-inhibitors will be discontinued from study treatment. These patients will be permitted to resume study visits for continued assessments (but not treatment with SEL-212 nor placebo) according to the institutional standards and/or procedures of the investigational site.

The categories of severity of illness (description and criteria) for COVID-19 are noted below as a reference:

Asymptomatic or Pre-symptomatic Infection: Individuals who test positive for COVID-19 but who have no symptoms that are consistent with COVID-19.

Mild Illness: Individuals who have any of the various signs and symptoms of COVID-19 (e.g., fever, cough, sore throat, malaise, headache, muscle pain, nausea, vomiting, diarrhea, loss of taste and smell) but who do not have shortness of breath, dyspnea, or abnormal chest imaging.

Moderate Illness: Individuals who show evidence of lower respiratory disease during clinical assessment or imaging and who have an oxygen saturation (SpO₂) ≥94% on room air at sea level.

Severe Illness: Individuals who have SpO₂ <94% on room air at sea level, a ratio of arterial partial pressure of oxygen to fraction of inspired oxygen (PaO₂/FiO₂) <300 mm Hg, respiratory frequency >30 breaths/min, or lung infiltrates >50%.

Critical Illness: Individuals who have respiratory failure, septic shock, and/or multiple organ dysfunction.

The Investigator will report a patient's positive test results for COVID-19 according to institutional standards and/or procedures.

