8.2 Patient Exclusion Criteria

A patient who meets any of the following criteria will be excluded from this study:

1. Has a history of anaphylaxis, severe allergic reactions, or severe atopy;
2. Has a history of any allergy to pegylated products, including, but not limited to pegloticase (Krystexxa®), peginterferon alfa-2a (Pegasys®), peginterferon alfa-2b (PegIntron®), pegfilgrastim (Neulasta®), pegaptanib (Macugen®), pegaspargase (Oncaspar®), pegademase (Adagen®), peg-epoetin beta (Mircera®), pegvisomant (Somavert®) certolizumab pegol (Cimzia®), naloxegol (Movantik®), peginesatide (Omontys®), and doxorubicin liposome (Doxil®);
3. Is taking and cannot discontinue known major CYP3A4/P-gp inhibitors or major CYP3A4/P-gp inducers at least 14 days before dosing. Patients must remain off these medications for the duration of the study, including natural products such as St. John's Wort or grapefruit juice.

4. Is taking drugs known to interact with rapamycin (sirolimus – Rapamune[®]) such as cyclosporine, diltiazem, erythromycin, ketoconazole, posaconazole, voriconazole, itraconazole, rifampin, verapamil unless they are stopped 14 days prior to dosing and will not be used/prescribed during the trial.
5. Had major surgery within 3 months of initial screening.
6. Had a gout flare during Screening that was resolved for less than 1 week prior to first treatment with study drug (exclusive of chronic synovitis/arthrits) unless the patient has a history of inter-flare intervals of < 1 week.
7. Has uncontrolled diabetes at Screening with HbA1c ≥ 8.5%;
8. Has fasting Screening glucose > 240 mg/dL
9. Has fasting Screening triglyceride > 500 mg/dL;
10. Has fasting Screening low-density lipoprotein (LDL) > 200 mg/dL;
11. Has glucose-6-phosphate dehydrogenase (G6PD) deficiency;
12. Has uncontrolled hypertension defined as blood pressure > 170/100 mmHg at Screening and 1 week prior to dosing
13. Individual laboratory values which are exclusionary
 - White blood cell count (WBC) < 3.0 x10⁹/L
 - Serum aspartate aminotransferase (AST) or alanine amino transferase (ALT) > 3x upper limit of normal (ULN) in the absence of known active liver disease
 - Estimated Glomerular filtration rate (eGFR) < 30 mL/min/1.73 m²
 - Urine-albumin-creatinine ratio (UACR) > 30 mg/g creatinine (conventional units) or > 3.39 mg/mmol creatinine (SI units)
 - Hemoglobin (Hgb) < 9 g/dL
 - Serum phosphate < 2.0 mg/dL

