17. Chemistry labs to include: Alkaline phosphatase, alanine aminotransferase (ALT), aspartate aminotransferase (AST), Total Bilirubin, blood urea nitrogen (BUN), Creatinine, UACR, eGFR, Fibrinogen, Glucose (fasting), Electrolytes (sodium, potassium, chloride, bi-carbonate, phosphate and magnesium).
18. Hematology labs to include: white blood cells (WBC) count with differential, Red blood cell (RBC) count, Hematocrit (Hct), Hemoglobin (Hgb), Platelet (Plt) count, and absolute neutrophil count (Abneu)
19. Coagulation labs to include: prothrombin time (PT), activated partial thromboplastin time (aPTT), international normalized ratio (INR)
20. Fasting lipid labs to include: total cholesterol, high density lipoprotein (HDL), low density lipoprotein (LDL), triglycerides
21. Collect sample prior to study drug dosing
22. Gout flares assessed based on validated gout flare definition ([Gaffo 2018](#))
23. Refer to [Section 11.3](#) for Health Questionnaires.
24. Start gout flare diary at Day 0 of Treatment Period 1.
25. Treatment Period 6 Day 28 assessments will be used for Treatment Period 7 Day 0 assessments. Do not repeat sample collection on Treatment Period 7 Day 0.

Abbreviations: CT: computed tomography; D (d): day; ECG: electrocardiogram; eGFR: estimated glomerular filtration rate; EOS: end of study; ET: early termination; h: hour; nAbs: neutralizing antibodies; PD: pharmacodynamic; RCTC: Rheumatology Common Toxicity Criteria; Scr: Screening Phase; sUA: serum uric acid; TP: treatment period; UACR: urine-albumin-creatinine ratio; ULT: urate lowering therapy

APPENDIX B SCHEDULE OF ASSESSMENTS: DOSING, SUA, AND URICASE ACTIVITY DURING THE DOUBLE-BLIND TREATMENT PHASE

Assessments	Day Timepoint	Treatment Periods: 1, 2, 3, 4, and 5				Treatment Period 6							
		D0 ¹				D0 ¹				D7 ²	D14 ²	D21 ²	D28 ³
		0h	~1.5h	~3.5h	~4.5h		0h	~1.5h	~3.5	~4.5h			
Premedicate: Infusion Reaction		X ⁴					X						
Blood Sample Uricase Activity		X ⁵			X ⁶	X	X ⁵			X ⁶	X	X	X
Blood Sample: sUA		X ⁵			X ⁶	X	X ⁵			X ⁶	X	X	X
Study Drug Infusion (Component 1) ⁷		X-----X ⁸					X-----X ⁸						
Study Drug Infusion (Component 2) ⁹			X ⁸ -----X					X ⁸ -----X					

1. Study drug dosing to occur 28 days from the previous dose with a window of -4 days to +3 day of the intended dosing day.
2. Assessments at this visit are permitted to be performed remotely (inclusive of collecting applicable lab draws and assessments per protocol visit windows).

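### The rule that accepts an unquantifiable urine albumin as an acceptable UACR has no urine creatinine condition, so with its example limit of 12 mg/dL it can pass patients above the 30 mg/g exclusion limit

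*Protocol*

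**What the plan says.** Exclusion criterion 13 in Protocol 8.2 lists "Urine-albumin-creatinine ratio (UACR) > 30 mg/g creatinine (conventional units) or > 3.39 mg/mmol creatinine (SI units") among the exclusionary laboratory values. The Synopsis and SAP 3.4.2 carry the same limit.

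Protocol 12.1.8.2 (Blood Chemistry) covers the case where the ratio cannot be calculated because microalbumin is "below the limit of quantification for the analytical method (eg. <12 mg/dL"). It then says that "the low microalbumin can be used as a surrogate for an acceptable UACR".

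No minimum urine creatinine is attached to that sentence, nor any check against 30 mg/g. It is not restricted to Screening either: UACR belongs to the chemistry panel ("blood urea nitrogen (BUN), Creatinine, UACR, eGFR, Fibrinogen, Glucose (fasting"), which Appendix A schedules at Screening and on treatment. The SAP does not mention the surrogate, and nothing else in either document restricts it.

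**The concern.** UACR is a ratio. A low albumin concentration bounds it only when the urine creatinine it is divided by is known. A rule that looks at albumin alone can therefore pass a patient whose ratio is above the limit, and the higher the albumin cut-off, the easier that becomes. The example of 12 mg/dL is high relative to a 30 mg/g ratio.

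The stake is renal safety at entry. Protocol 12.2.1.5 makes worsening renal function tests and proteinuria adverse events of special interest when judged clinically significant, and Protocol 6.2.5 names UACR among the safety assessments. UACR is the only albuminuria threshold in the eligibility criteria. Because the sentence is not limited to Screening, an on-treatment result below the limit of quantification would also be read as acceptable.

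**Working it through.** **Inputs**

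- UACR exclusion limit: above 30 mg/g, or above 3.39 mg/mmol (Protocol 8.2, criterion 13).
- Example limit of quantification: 12 mg/dL (Protocol 12.1.8.2).
- Urine creatinine: not given in the documents. A range of 50 to 300 mg/dL is assumed.
- Creatinine molar mass: 113.12 g/mol, a physical constant used only for the unit check.

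**Step 1: is the exclusion limit internally consistent?**

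30 mg/g × 113.12 g/mol ÷ 1000 = 3.394 mg/mmol, which reproduces the protocol's 3.39. The two forms of the limit agree, so the difficulty is not there.

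**Step 2: the creatinine at which the surrogate is safe**

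UACR (mg/g) = 1000 × albumin (mg/dL) ÷ creatinine (mg/dL).

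With albumin at 12 mg/dL and UACR at 30 mg/g, creatinine = 1000 × 12 ÷ 30 = 400 mg/dL. Below that concentration, some albumin values under 12 mg/dL give a UACR above 30 mg/g.

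With 12 mg/L, which is 1.2 mg/dL, creatinine = 1000 × 1.2 ÷ 30 = 40 mg/dL.

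**Step 3: the largest UACR that could pass, under each unit**

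The second column is 30 × creatinine ÷ 1000. The third and fifth are 1000 × 12 ÷ creatinine and 1000 × 1.2 ÷ creatinine. They are upper bounds, approached when albumin lies just under the limit.

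| Urine creatinine, assumed (mg/dL) | Albumin at which UACR is 30 mg/g (mg/dL) | Bound if the limit is 12 mg/dL (mg/g) | Multiple of 30 mg/g | Bound if the limit is 12 mg/L (mg/g) |
|---|---|---|---|---|
| 50 | 1.5 | 240 | 8 | 24 |
| 100 | 3 | 120 | 4 | 12 |
| 150 | 4.5 | 80 | 2.7 | 8 |
| 200 | 6 | 60 | 2 | 6 |
| 300 | 9 | 40 | 1.3 | 4 |

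**Step 4: what a single result can mean**

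Take creatinine at 100 mg/dL and the limit at 12 mg/dL. Albumin of 2 mg/dL gives 1000 × 2 ÷ 100 = 20 mg/g, which is eligible. Albumin from just above 3 up to 12 mg/dL gives just above 30 up to 120 mg/g, which criterion 13 excludes. Both are reported as below the limit of quantification, and the surrogate treats them alike.

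Under the mg/L reading the gap remains only in dilute urine. At creatinine 20 mg/dL the bound is 1000 × 1.2 ÷ 20 = 60 mg/g.

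**The case against.** The strongest reply is that 12 mg/dL is not the rule. It is a parenthetical example. The operative trigger is the laboratory's actual limit of quantification, which neither document states; Protocol 12.1.8 refers sample processing to the Study Operations Manual. If the real limit is low, or if mg/L was meant, few or no ineligible patients pass. This stands, and it is why the size has to be given under both units. It does not remove the point: 12 mg/dL is the only figure the protocol gives, and the missing creatinine condition is a gap whatever the number.

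Four stronger readings are tempting, and the documents do not support them.

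- **Every patient below 12 mg/dL is far above 30 mg/g.** The 12 mg/dL is an upper bound on the patient's albumin, and many such patients would be within the limit. At creatinine 300 mg/dL even the bound is only 1.3 times the limit.
- **The two limits contradict each other, so one must be wrong.** One is an assay property and the other an eligibility threshold. Both can be true of an insensitive assay. The fault lies in using the first as a stand-in for the second without creatinine.
- **The surrogate nullifies criterion 13.** The UACR item still excludes anyone with quantifiable albumin and a ratio above 30 mg/g, and the other items of criterion 13, including eGFR, are untouched. Screening urinalysis and the investigator-judgment criterion (27) also remain, and the surrogate is worded as permitted, not required.
- **The surrogate distorts the baseline for the laboratory shift tables.** Protocol 12.1.8.2 does not say that any value is entered into the analysis data, and SAP 10.4 does not mention the surrogate. An unquantifiable albumin leaves the ratio uncalculable with or without this sentence, so any loss there comes from the assay.

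**Conclusion.** The point holds in a bounded form. As written, the surrogate can admit patients whom criterion 13 excludes, because it ignores urine creatinine. If 12 mg/dL is the real limit, this is possible at any urine creatinine below 400 mg/dL, and over the assumed 50 to 300 mg/dL the largest ratio that could pass runs from 240 down to 40 mg/g. If mg/L was intended, the corresponding maximum is 24 down to 4 mg/g, and the problem is confined to creatinine below 40 mg/dL.

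The size rests on two unknowns: the laboratory's actual limit with its unit, and the patients' urine creatinine. The number of patients affected cannot be estimated from the documents. The consequence is for eligibility and renal safety. The sample size and the primary analysis are not affected.

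**What to change.** Confirm with the central laboratory the actual limit of quantification for urine microalbumin, and correct the value or unit in Protocol 12.1.8.2 if needed. Then reconcile that section with criterion 13: accept the surrogate only when the limit of quantification divided by the measured urine creatinine, expressed in mg/g, does not exceed the UACR limit the protocol already states. This brings in no new clinical threshold.

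The cost is one query to the laboratory and one sentence in the protocol. No extra sample or test is required, because urine creatinine is needed for the ratio anyway.

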12.1.8.8 Serology

Serology screening will include human immunodeficiency virus (HIV) antibodies 1 and 2, hepatitis-B surface antigen (HBsAg), and hepatitis-C antibody (HCVAAb).

12.1.8.9 Drug Screen

Urine drug screen will include amphetamines, barbiturates, benzodiazepines, cocaine, and opiates.

12.1.8.10 Pregnancy Screen

Samples for urine pregnancy testing (hCG) will be obtained.

Male patients of reproductive potential who are having intercourse with female partners of childbearing potential must agree to use 2 forms of contraception, 1 of which must be a barrier method, during the study and for 4 months after the last study drug administration. Acceptable barrier methods include a condom and diaphragm. Acceptable forms of birth control for female partners of childbearing potential are non-hormonal and hormonal intrauterine devices, hormonal birth control pills, hormonal birth control patches, hormonal birth control injections, hormonal birth control implants. Spermicide used alone is not an acceptable method and must be used with another acceptable form birth control method. Abstinence is acceptable if consistent with the patient's normal lifestyle.

Female patients are required to have negative hCG test results throughout the study. If a female patient becomes pregnant after she begins taking study drug, the procedures in [Section 12.2.2.7](#) should be followed.

In addition, for any reported case of delayed menstrual period (over 1 month between menstruations) and for those women with infrequent or irregular menstrual cycles, confirmation of absence of pregnancy should occur.

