7.1.1 Screening Phase

After providing written informed consent, the patient is considered enrolled in the study. Patients will be evaluated for inclusion during the Screening Phase. For all patients, the standard Screening Phase will be up to 45 days prior to Baseline. The Screening Phase may be initiated by a preliminary screening with an abbreviated informed consent focused on COVID-19 testing and serum uric acid levels followed by providing study-wide informed consent and the remainder of screening assessments if determined to proceed. **Of note**, if the sUA level obtained during preliminary screening meets eligibility requirements

(i.e., ≥ 7 mg/dL), the sUA should **not** be repeated during the subsequent complete screening assessment. Concurrently with the Screening Phase, a premedication period for potential gout flare with colchicine (or non-steroidal anti-inflammatory drug [NSAID], if colchicine is contraindicated) of at least 7 days prior to Baseline will be required for all patients, and a washout period of at least 7 days will be required prior to Baseline for patients on any urate-lowering therapy (ULT). Both the ULT washout period and the gout flare prophylaxis period may be started earlier than 7 days prior to Baseline. At the discretion of the PI, chronic refractory gout patients whose sUA is lower than the eligibility level of ≥ 7 mg/dL on prescreening or initial screen, may undergo ULT washout prior to retesting the sUA. Initiation of gout flare prophylaxis with colchicine (or non-steroidal anti-inflammatory drug [NSAID], if colchicine is contraindicated) can also be considered coincidentally with the ULT washout to prevent a potential gout flare.

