8. SELECTION AND WITHDRAWAL OF PATIENTS

8.1 Patient Inclusion Criteria

A patient must meet all the following criteria to be eligible for this study:

1. Has provided written informed consent prior to the conduct of any study specific procedures;
2. Understands and is willing and able to comply with study requirements, including the schedule of follow-up visits;
3. Has negative results of an FDA Emergency Use Authorized COVID-19 molecular assay for detection of SARS-CoV-2 RNA from a nasal or oropharyngeal specimen;
4. Has a history of symptomatic gout defined as:
 - o ≥ 3 gout flares within 18 months of Screening or
 - o Presence of ≥ 1 gout tophus or
 - o Current diagnosis of gouty arthritis
5. At the Screening Visit male age 19 – 80 years, inclusive or female of non-childbearing potential age 19-80 years, inclusive, where non-childbearing potential is defined as:
 - o > 6 weeks after hysterectomy with or without surgical bilateral salpingo-oophorectomy or
 - o Post-menopausal (> 24 months of natural amenorrhea or in the absence of >24 months of amenorrhea, 1 documented confirmatory FSH measurement)
6. Has chronic refractory gout defined as having failed to normalize sUA and whose signs and symptoms are inadequately controlled with any of the xanthine oxidase inhibitors, either allopurinol and/or febuxostat, at the medically appropriate dose, or for whom these drugs are contraindicated for the patient
7. Has at Screening sUA ≥ 7 mg/dL
8. Has not participated in a clinical trial within 30 days of the Screening Visit and agrees to not participate in a clinical trial for the duration of the study;
9. Negative serology for HIV-1/-2 and negative antigen to hepatitis B and negative antibodies to hepatitis C.

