20. APPENDICES

APPENDIX A SCHEDULE OF ASSESSMENTS: DOUBLE-BLIND TREATMENT PHASE

Assessment	Scr. - 45 d to D0 (Pre-dose) ³	Double-Blind Treatment Phase														EOS ¹	ET	
		TP1 ²		TP2 ²		TP3 ²		TP4 ²		TP5 ²		TP6 ²						
		D0	D21 ⁴	D0 ⁵	D7 ⁴	D14 ⁴	D21 ⁴	D28 ^{5,25}										
Informed Consent	X																	
Demographics	X																	
Inclusion/Exclusion	X																	
Medical History	X																	
Chest X-Ray	X															X	X	
Multi-energy CT ⁶	X							X								X	X	
Physical Examinations	X ⁷	X ⁸		X ⁸		X ⁸		X ⁸		X ⁸		X ⁸				X ⁷	X ⁷	
Vital Signs	X	X ⁹		X ⁹		X ⁹		X ⁹		X ⁹		X ⁹		X	X		X	
Weight and Height ¹⁰	X		X		X		X		X		X			X	X		X	
12-Lead ECG	X															X	X	
Screening Labs ¹¹	X																	
COVID-19 Testing	X																	
Urine Pregnancy Test	X																	
Washout: ULTs	X ¹³	Patients will abstain from ULT use after the ULT washout period																
Document ULTs Discontinued	X																	
Dispense Premedication: Gout Flare and Infusion Reaction ¹²	X		X		X		X		X		X				X			
Premedication: Gout Flare	X ¹⁴																	
Randomization	X ¹⁵ <-----> X ¹⁵																	
Premedication: Infusion Reaction		X ¹⁶		X ¹⁶		X ¹⁶		X ¹⁶		X ¹⁶		X ¹⁶						
Safety Labs: Chemistry ¹⁷	X	X	X		X		X		X		X				X	X	X	
Safety Labs: Hematology ¹⁸	X	X	X		X		X		X		X			X	X		X	
Safety Labs: Coagulation ¹⁹	X	X	X		X		X		X		X			X	X		X	
Safety Labs: Lipids ²⁰	X	X	X		X		X		X		X			X	X		X	
Safety Labs: eGFR ¹⁷	X	X	X		X		X		X		X			X	X		X	
Blood Sample for Anti-Pegadricase ²¹		X	X	X	X	X	X	X	X	X	X	X			X	X	X	
Blood Sample for nAbs ²¹		X	X	X	X	X	X	X	X	X	X	X			X	X	X	
Blood Sample for Anti-Pegadricase POC Validation ²¹		X	X	X	X	X	X	X	X	X	X	X			X	X	X	
Blood Sample for Anti-Uricase ²¹		X	X	X	X	X	X	X	X	X	X	X			X	X	X	
Blood Sample for Biomarkers ⁶		X		X		X							X	X		X	X	

Blood Sample for Multiomic Markers		X		X		X		X		X	X			X		X
Blood Sample for HLA Typing			X													
Blood Sample for T Cell Analysis		X								X	X			X		X

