15 DECEMBER 2022

APPENDIX C SCHEDULE OF ASSESSMENTS: DOUBLE-BLIND EXTENSION PHASE

Assessment	Double-Blind Extension Phase												EOS ¹	ET	
	TP7 ²		TP8 ²		TP9 ²		TP10 ²		TP11 ²		TP12 ²				
Day	D0 ^{4,18}	D21 ³	D0 ⁴	D21 ³	D0 ⁴	D21 ³	D0 ⁴	D21 ³	D0 ⁴	D21 ³	D0 ⁴	D21 ³	D28 ⁴		
Chest X-Ray	X													X	X
Multi-energy CT ⁵	X													X	X
Physical Examinations	X ⁶		X ⁷		X ⁷		X ⁷		X ⁷		X ⁷		X ⁶		X ⁶
Vital Signs	X ⁸		X ⁸		X ⁸		X ⁸		X ⁸		X ⁸	X	X		X
Weight		X		X		X		X		X		X	X		X
12-Lead ECG	X													X	X
COVID-19 Testing	As clinically indicated. Refer to Section 12.1.8.7														
Dispense Premedication: Gout Flare and Infusion Reaction ⁹		X		X		X		X		X		X			
Premedication: Gout Flare	Continuously														
Premedication: Infusion Reaction	X ¹⁰		X ¹⁰		X ¹⁰		X ¹⁰		X ¹⁰		X ¹⁰				
Safety Labs: Chemistry ¹¹	X	X		X		X		X		X		X	X		X
Safety Labs: Hematology ¹²	X	X		X		X		X		X		X	X		X
Safety Labs: Coagulation ¹³	X	X		X		X		X		X		X	X		X
Safety Labs: Lipids ¹⁴	X	X		X		X		X		X		X	X		X
Safety Labs: eGFR ¹¹	X	X		X		X		X		X		X	X		X
Blood Sample for Anti-Pegadricase ¹⁵	X	X	X	X	X	X	X	X	X	X	X	X	X		X
Blood Sample for nAbs ¹⁵	X	X	X	X	X	X	X	X	X	X	X	X	X		X
Blood Sample for Anti-Pegadricase POC Validation ¹⁵	X	X	X	X	X	X	X	X	X	X	X	X	X		X
Blood Sample for Anti-Uricase ¹⁵	X	X	X	X	X	X	X	X	X	X	X	X	X		X
Blood Sample for Biomarkers ⁵	X											X			X
Blood Sample for Multiomic Markers	X				X							X		X	X
Blood Sample for T Cell Analysis	X											X		X	X
Tophus Assessment/Photography	X						X							X	X
Gout Flare Assessment ¹⁶	X		X		X		X		X		X		X		X
Gout Flare Weekly Diary	Continuously on Weekly Basis														
Joint Assessment (tenderness, swelling)	X						X						X		X
Health Questionnaires ¹⁷	X						X						X		X
Collect Sample for sUA	Refer to Schedule of Assessments (Appendix D) for sUA Sample Collection during Treatment Phase														X
PD/Uricase Activity Assessment	Refer to Schedule of Assessments (Appendix D) for PD/Uricase Activity Assessments during Treatment Phase														X
Study Drug Administration	Refer to Schedule of Assessments in Appendix D for Study Drug Administration during the Treatment Phase														
Infusion Reaction Follow-up	Refer to Section 12.2.1.5														

Concomitant Medications / Procedures	Continuously	X	X
AE Collection	Continuously	X	X
SAE Collection	Continuously	X	X

[figure not shown]
[figure not shown]

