**TABLE C: SCHEDULE OF ASSESSMENTS FOR BLINDED EXTENSION PHASE**

Assessment	Double-Blind Extension Phase												EOS 	ET
	TP7 		TP8 		TP9 		TP10 		TP11 		TP12 			
Day	D0 	D21 	D0 	D21 	D0 	D21 	D0 	D21 	D0 	D21 	D0 	D21 	D28 	
Chest X-Ray	X												X	X
Multi-energy CT 	X												X	X
Physical Examinations	X 		X 		X 		X 		X 		X 		X 	X 
Vital Signs	X 		X 		X 		X 		X 		X 	X	X	X
Weight		X		X		X		X		X		X	X	X
12-Lead ECG	X												X	X
COVID-19 Testing	As clinically indicated. Refer to Protocol Section 12.1.8.7													
Dispense Premedication: Gout Flare and Infusion Reaction 		X		X		X		X		X		X		
Premedication: Gout Flare	Continuously													
Premedication: Infusion Reaction	X 		X 		X 		X 		X 		X 			
Safety Labs: Chemistry 	X	X		X		X		X		X		X	X	X
Safety Labs: Hematology 	X	X		X		X		X		X		X	X	X
Safety Labs: Coagulation 	X	X		X		X		X		X		X	X	X
Safety Labs: Lipids 	X	X		X		X		X		X		X	X	X
Safety Labs: eGFR 	X	X		X		X		X		X		X	X	X
Blood Sample for Anti-Pegadricase 	X	X	X	X	X	X	X	X	X	X	X	X		X
Blood Sample for nAbs 	X	X	X	X	X	X	X	X	X	X	X	X	X	X
Blood Sample for Anti-Pegadricase POC Validation 	X	X	X	X	X	X	X	X	X	X	X	X		X
Blood Sample for Anti-Uricase 	X	X	X	X	X	X	X	X	X	X	X	X		X
Blood Sample for Biomarkers 	X										X			X
Blood Sample for Multiomic Markers	X			X							X		X	X
Blood Sample for T Cell Analysis	X										X		X	X
Tophus Assessment/Photography	X					X							X	X
Gout Flare Assessment 	X		X		X		X		X		X		X	X
Gout Flare Weekly Diary	Continuously on Weekly Basis													
Joint Assessment (tenderness, swelling)	X					X						X		X
Health Questionnaires 	X					X						X		X
Collect Sample for sUA	Refer to Schedule of Assessments ( Appendix D ) for sUA Sample Collection during Treatment Phase													X

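### The protocol requires negative hCG results throughout the study but schedules one urine test, at Screening; in practice the gap concerns only women admitted as post-menopausal on a single FSH value

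*Protocol*

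**What the plan says.** Section 12.1.8.10 of the protocol sets the rule without giving test times: "Female patients are required to have negative hCG test results throughout the study". It adds a check driven by menstrual signs. One limb applies after any reported delayed period. The other reads: "for those women with infrequent or irregular menstrual cycles, confirmation of absence of pregnancy should occur". Neither limb names a test, a visit or an interval.

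Timing is left to the schedules. Section 12.1.8 says: "All laboratory assessment will be conducted according to the schedule described in" Appendices A and C.

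- Appendix A has a row "Urine Pregnancy Test" with a single mark, in the Screening column. Treatment Periods 1 to 6, End of Study and Early Termination are blank.
- The extension table, "APPENDIX C SCHEDULE OF ASSESSMENTS: DOUBLE-BLIND EXTENSION PHASE", has no pregnancy-test row.
- SAP Table A repeats the single Screening mark, and "TABLE C: SCHEDULE OF ASSESSMENTS FOR BLINDED EXTENSION PHASE" also has no row.

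SAP Section 10.4 nevertheless plans a listing of pregnancy test results from the treatment and extension phases.

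Inclusion criterion 5 (Section 8.1) limits female entry to women of non-childbearing potential: those who have had a hysterectomy and those who are post-menopausal. A woman can count as post-menopausal on this basis: "in the absence of >24 months of amenorrhea, 1 documented confirmatory FSH measurement". Section 12.1.8.11 adds that an FSH value in the postmenopausal range may serve as confirmation in women who are not on hormonal contraception or hormone replacement.

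**The concern.** A site that does exactly what the schedule asks holds one hCG result per woman, obtained before the first dose. It cannot then show negative results over the following year of dosing, and the SAP listing has no scheduled source of on-treatment data.

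For most eligible women this is only a matter of wording, because they cannot become pregnant. The exception is a woman who still has ovaries, tubes and uterus, has not gone more than 24 months without menses, and qualifies on one FSH measurement. Her status rests on a single laboratory value. If she is randomized to active treatment she may receive up to 12 infusions containing rapamycin with no scheduled pregnancy test after Screening. What is at stake is the safety of a very small group, and the credibility of a safety rule that the schedule does not deliver. Efficacy conclusions are not involved.

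**Working it through.** The plan gives no figure to reproduce. The check is a count of scheduled tests, an interval, and a rough size for the group.

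**1. Scheduled urine hCG tests**

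| Schedule | Screening | Treatment periods | EOS / ET |
|---|---|---|---|
| Protocol Appendix A, SAP Table A (TP1-6) | 1 | 0 of 6 | 0 |
| Protocol Appendix C, SAP Table C (TP7-12) | – | 0 of 6 | 0 |

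The total is 1 test, before dosing, against up to 12 doses. The protocol and SAP tables agree, and the row is absent from both extension tables, so a fault in reading the PDF is an unlikely explanation.

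**2. Interval from the only test to the last dose**

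Doses are 28 days apart, so dose 12 falls 11 × 28 = 308 days after dose 1. On Screening, Section 7.1.1 says: "For all patients, the standard Screening Phase will be up to 45 days prior to Baseline". The interval is therefore 308 days if the test is done at Baseline and 45 + 308 = 353 days if it is done at the start of Screening.

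This is the nominal range. Section 7.4.1.1 allows a treatment period to run to 90 days, and one such period would add 90 − 28 = 62 days, giving 353 + 62 = 415. In the other direction, the sUA stopping rule ends dosing early for some patients, so 12 doses is a maximum.

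**3. How many women**

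Protocol Section 7.6.3.2.2 reports 7 women among 170 patients in study 202. Its eligibility rules are not given, so this is only a guide.

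- Expected women here: 120 × 7/170 = 4.9.
- Predictive 2.5-97.5% range (beta-binomial, Jeffreys prior, Beta(7.5, 163.5), n = 120): 1 to 12.

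The share entering by FSH is not given. I assume 10%, 25% and 50%. The probability that no such woman is enrolled is the average of (1 − s)^k over the predictive distribution of k women, where s is the share. For active drug, s is replaced by s × 2/3, because allocation is 1:1:1 and one arm is saline.

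| Assumed FSH share | Expected FSH-route women (4.9 × share) | P(none enrolled) | P(none receives active drug) |
|---|---|---|---|
| 10% | 0.5 | 0.60 | 0.71 |
| 25% | 1.2 | 0.29 | 0.43 |
| 50% | 2.5 | 0.10 | 0.20 |

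**4. Testing load of the fix**

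Up to 12 tests per woman: 12 × 0.5 = 6 to 12 × 2.5 = 30 expected. At the top of both ranges, 12 women × 50% × 12 tests = 72.

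**The case against.** The best defence is that eligibility already handles the risk. Every woman must be of non-childbearing potential, the Screening test comes on top of that, and the FSH value has to lie in the postmenopausal range in a woman not on hormonal therapy. This largely stands. It is why the practical gap shrinks to one entry route and why the point is minor. A reader might infer that women able to conceive are being dosed for a year untested. The documents do not support that, because criterion 5 excludes them.

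A second defence is that the menstrual-sign check covers the remaining group. In part it does: an FSH-route woman who still menstruates would usually fall under one of its limbs, and pregnancies must be reported and followed up (Section 12.2.2.7). But the check has no stated test, visit or interval and no place in the schedule, and a missed period is a weak signal in a woman whose periods are already stopping.

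A third defence reads the sentence as meaning that any hCG obtained must be negative, and the SAP listing as output for whatever unscheduled results arise. That is possible, but it fits poorly with a requirement covering the whole study.

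On proportion, monthly testing of every woman, or of everyone without a hysterectomy or long amenorrhea, would be excessive. Section 12.1.8.11 treats bilateral salpingectomy and bilateral oophorectomy as permanent sterilization, and testing those women serves no purpose. That objection stands and sets the scope of the fix.

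**Conclusion.** The inconsistency is real and is wrong as written: the rule runs throughout the study, the SAP expects on-study results, and the schedules provide one pre-dose test. Its weight is minor. If study 202 is a guide, about 5 of 120 patients would be women. At assumed FSH-route shares of 10% to 50%, between 0.5 and 2.5 of them would be in the affected group, and the chance that none of these receives active drug is about 71% down to 20%. Those shares are assumptions with no source in the documents. For any woman who is affected, the nominal gap from the only scheduled test to the last dose is 308 to 353 days, and longer if periods are extended.

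Two stronger readings should be resisted. The 353 days is neither a maximum nor a typical exposure, since extensions lengthen it, the stopping rule shortens it, and one third of patients receive saline. Nor does the point bear on any endpoint, the sample size or the efficacy analysis.

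**What to change.** Add a pre-dose urine hCG row at the existing Day 0 visits of Treatment Periods 1 to 12, in Protocol Appendices A and C and SAP Tables A and C. Limit it to women who enter by the FSH route and are not permanently sterile (no hysterectomy, bilateral salpingectomy or bilateral oophorectomy), for as long as they are dosed.

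Reword Section 12.1.8.10 to match: a negative urine hCG at Screening for all women, a negative pre-dose urine hCG for this subgroup, and the menstrual-sign check as it is now. The listing in SAP Section 10.4 then has a defined source. Rewording alone would remove the contradiction but leave this subgroup without a scheduled test.

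The testing cost is a handful of dipsticks, possibly none, at infusion visits already held on site. The administrative cost is a protocol amendment with IRB/IEC approval across approximately 40 centers (Section 15.3), so it should be bundled with another amendment. The documents do not show whether dosing is still under way. If it has ended, what remains is to correct the text and state in the report that no on-treatment test was scheduled.
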